3.2 Study Population

All patients enrolled must be newly prescribed golimumab per the usual standard of care of the investigator.

In patients who have been prescribed these agents the moment of prescription is normally separated from the moment the agents are administered (e.g. administrative procedures, day-clinic visit to be scheduled, retrieval of the medicine at the pharmacist, etc.). Patients will be enrolled after the decision to treat with golimumab is made, but before the initiation of the newly prescribed medicine, i.e. patients must not have initiated treatment prior to the baseline data collection (enrollment).

Patient's data are to be collected after signing informed consent form and till the end of the study. If patient discontinues participation earlier, the data before discontinuation will be collected.

Patient can withdraw the informed consent form for any reason for any time. Investigator can decide to discontinue participation of patient for safety, lack of efficacy or any other reason.

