4.2 Treatment of golimumab and end of treatment

Data on golimumab usage as well as reasons for discontinuation of treatment will be collected at baseline and at 6, 12, 18, 24 months.

Reasons for discontinuation are withdrawal of the informed consent form by the patient for any reason, decision of the investigator to stop administration of golimumab due to safety concerns and/or due to lack of efficacy.

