6.1.2. Other Procedures

6.1.2.1. Withdrawal/Discontinuation

The patient may withdraw his/her consent to participate in the study at any time for any reason. This decision will not have any consequences for his/her future medical care.

The investigator may exclude a patient from the study at any time if he/she finds that continuation of participation in the study might be harmful or does not meet interests of the patient: for safety, lack of efficacy or any other reason.

The sponsor may stop the study at any time. In such case, all investigators will be informed in advance.

Product: MK-8259
Protocol/Amendment No.: 021
VEAP ID NO: 6189
Date: 15-January-2018

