6.1.3.3. Radiographic stage of sacroiliitis

Radiological stage of sacroiliitis (I, II, III, IV) will be recorded at baseline.

6.1.3.4. Golimumab administration registration.

Data on golimumab usage as well as reasons for discontinuation of treatment will be collected at baseline and at 6, 12, 18, 24 months.

Reasons for discontinuation are withdrawal of the informed consent form by the patient for any reason, decision of the investigator to stop administration of golimumab due to safety concerns and/or due to lack of efficacy.

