8.3 Sample Size and Power Calculations

Sample size calculation is based on data from GO-RAISE registrational study in which golimumab was evaluated in patients with AS [18-21]. The baseline BASFI was 5.0 which changed by mean (\pm SD, standard deviation) $-2.5 (\pm 2.12)$ at week 52 (approximately 12 months) [19].

Sample size formula evaluation is $n = f(\alpha, \beta/2) \times 2 \times \sigma^2/d^2$ where:

n is sample size;

α is type 1 error = 5%;

β is type 2 error = 10%;

σ is standard deviation;

d is equivalents limit;

$f(\alpha, \beta) = [\Phi-1(\alpha) + \Phi-1(\beta)]^2$ where Φ is cumulative distribution function for the normal distribution.

Product: MK-8259
Protocol/Amendment No.: 021
VEAP ID NO: 6189
Date: 15-January-2018

Power of the study is 90% with formula evaluation $P = 1-\beta$ where:

P is power;

β is type 2 error = 10%.

Thus, the analysis of the data shows that the minimum necessary sample size should be at least 18 patients to show a statistically significant change of BASFI from baseline to 12 months.

On this basis and considering that the dropout rate over the two years of the study is expected to be about 30% (ranging from 21% in a randomized controlled study [19] to 37% in real clinical practice [25]), it is decided that the necessary number of patients to be included into the study should be 39 individuals. It is expected that at least 27 patients will be included in the patient set completing the study.

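### Stopping golimumab and leaving the study are not clearly separated, so a patient removed for lack of efficacy can enter the BASFI analysis with an earlier, carried-forward value

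*Combined protocol and SAP*

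**What the plan says.** **Leaving the study.** Section 3.2 sets the default: "Patient's data are to be collected after signing informed consent form and till the end of the study". It then gives the exception: "If patient discontinues participation earlier, the data before discontinuation will be collected". The grounds are broad: "Investigator can decide to discontinue participation of patient for safety, lack of efficacy or any other reason". Section 6.1.2.1 repeats them for patients for whom continuing might be harmful or "does not meet interests of the patient: for safety, lack of efficacy or any other reason".

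**Stopping the drug.** Sections 4.2 and 6.1.3.4 have the same text on treatment: "Data on golimumab usage as well as reasons for discontinuation of treatment will be collected at baseline and at 6, 12, 18, 24 months". The list that follows mixes a study exit with treatment decisions: "Reasons for discontinuation are withdrawal of the informed consent form by the patient for any reason, decision of the investigator to stop administration of golimumab", the latter for safety or lack of efficacy. No section says what is collected after golimumab is stopped in a patient who has not withdrawn consent.

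**Missing outcomes.** Sections 2.3, 8.2.1 and 8.2.2 fill missing values by LOCF. Section 2.3 names months 6 and 18 as the sources for months 12 and 24, and 8.2.2 also allows the visit after a missed one. Section 8.2.2 adds a separate evaluation of completers and dropouts.

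**Dropout.** Section 8.3 assumes about 30% over two years, "ranging from 21% in a randomized controlled study [19] to 37% in real clinical practice [25"]. Going by its title in section 11, reference 25 is a registry report on two-year golimumab retention in three diseases.

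**The concern.** This is a single-arm study whose main product is the size of the BASFI change. Lack of efficacy is a permitted ground for ending participation, and collection ends with participation. Whether a month-12 or month-24 value exists can then depend on how the patient is doing. The replacement comes from an earlier visit, possibly before the failure that led to removal.

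Section 8.2.1 names early dropout as a source of bias. Its remedies are an interim analysis, which recovers no missing value, and LOCF. The comparison of completers with dropouts cannot test LOCF, because dropouts have no later value to test it against.

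The gap is largely avoidable. Section 3.1 requires no study procedure, and section 4.3 says that these scores are available for most AS patients in routine practice. For a patient who stops the drug but stays with the same clinic, the outcome may already be in the chart. Without a stated rule, sites may handle such patients differently.

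**Working it through.** **1. The plan's own figures.** 27 / 0.70 = 38.6, so 39 enrolled, and 39 x 0.70 = 27.3 completers: both agree with 8.3. The minimum of 18 is reproduced only approximately. The printed formula with SD 2.12 and d = 2.5 gives 18.7 (two-sided 5%, beta/2), 15.6 (one-sided 5%, beta/2) or 15.1 (two-sided 5%, beta 10%). Nothing below depends on this.

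**2. Patients without an observed month-24 value** (dropout rates from 8.3):
- 21%: 39 x 0.21 = 8.2
- 30%: 39 x 0.30 = 11.7
- 37%: 39 x 0.37 = 14.4

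**3. Patients without an observed month-12 value.** The plan gives no timing of exits. Assume a constant exit rate, so the share gone by month 12 is 1 - sqrt(1 - D), where D is two-year dropout:
- D = 0.21: 0.111, or 4.3 patients
- D = 0.30: 0.163, or 6.4 patients
- D = 0.37: 0.206, or 8.0 patients

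The upper bound, with every exit before month 12, is the set of counts in step 2: about 12 patients at 30%.

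**4. Effect on the month-12 mean.** Completers change by -2.5 (8.3). Assume that leavers are truly back at baseline (0) and that LOCF carries -1.0.
- Constant exit rate, 16% imputed. LOCF: 0.84 x (-2.5) + 0.16 x (-1.0) = -2.26. True: 0.84 x (-2.5) = -2.10. The excess is 0.16 / 2.10, about 8%.
- All exits before month 12, 30% imputed. LOCF: 0.70 x (-2.5) + 0.30 x (-1.0) = -2.05. True: 0.70 x (-2.5) = -1.75. The excess is 0.30 / 1.75, about 17%.

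**5. Range for the assumed gap.** The error in the mean is the share imputed times the gap between true and carried values. For a gap of 0.5 to 2.5 BASFI points:
- 16.3% imputed: 0.163 x 0.5 = 0.08 to 0.163 x 2.5 = 0.41 points
- 30% imputed: 0.30 x 0.5 = 0.15 to 0.30 x 2.5 = 0.75 points

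**6. Direction.** A patient who leaves before month 6 has only baseline to carry, and the plan does not say whether baseline is carried. If it is, the fill is zero change: no overstatement for a patient truly back at baseline, and an understatement for one who has improved.

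**7. Significance.** Paired t-test power at a change of -2.5 and SD 2.12 is 99.7% with 18 patients. If 30% of the 39 were truly at zero change, the mean would be -1.75 and the SD sqrt(2.12^2 + 0.3 x 0.7 x 2.5^2) = 2.41, and power would still be 99.3%. The estimate is exposed; the test is not.

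**The case against.** The strongest reply is that the plan nowhere says stopping golimumab ends participation. The sentence on collecting earlier data is about participation, and the one before it runs collection to the end of the study. Golimumab use is recorded at every visit, which suits a patient who stays in the study off drug. Section 8.1 lists attrition separately from reasons for discontinuation. The CRF is still to be developed (6.1.2.2), so it may yet hold separate items. All of this stands. A reader might infer that the plan treats the two events as one, but the documents show only that it does not separate them clearly.

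A reader might also take the 37% as proof that drug stopping is counted as study dropout. Only the title of that source is visible, and the 21% comes from a different kind of study. A retention figure borrowed for planning does not show how stoppers will be followed.

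Nor do the documents support the inference that no all-patient result or check is possible. An all-patient LOCF result is planned, and model-based or tipping-point checks need no post-exit data. What cannot be done is to compare LOCF with observed post-exit values.

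Finally, the objectives concern change on golimumab therapy, and values after stopping may reflect other treatment. That is a good reason not to change the main analysis. It is no reason to leave the values uncollected.

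**Conclusion.** The concern holds in limited form. Under the stated rules, a patient may be removed for lack of efficacy, collection then ends, and an earlier value takes the place of the outcome. Whether this also happens to patients who only stop the drug is left open.

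Between 8 and 14 of 39 patients would lack an observed month-24 BASFI. At 30% dropout, about 6 would lack the primary month-12 value, and at most about 12. The likely overstatement at month 12 is modest, about 8% under the assumed values in step 4. The 17% figure should not be read as the expected error in the primary endpoint: it places the whole two-year dropout before month 12 and gives every leaver a carried value of -1.0. Exit timing, leavers' true status and the carried value are all assumptions. Not every leaver is a treatment failure, since safety and consent withdrawal for any reason are also listed, so the sign of the error is uncertain too. The primary test would very probably be significant either way.

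**What to change.** - In 4.2, 6.1.3.4 and the CRF, record golimumab stopped (date, reason) and left the study (date, reason) as separate items, and take consent withdrawal out of the list of reasons for stopping treatment.
- In 3.2, state that patients who stop golimumab but keep their consent continue routine data collection to month 24.
- In section 8, keep the on-therapy objective and add an analysis of all observed month-12 and month-24 BASFI values, regardless of golimumab status, as a sensitivity analysis to LOCF.

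A reader might go further and make the observed-value analysis in all enrolled patients primary. That would change the question set in 2.1 and 8.1.2, and this point does not require it.

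The cost is protocol wording, two CRF items and extra chart abstraction for at most about 8-14 patients. The number will be lower, since patients who withdraw consent cannot be followed. Values after stopping need care in interpretation because other treatment may have started. No procedure is added and no treatment decision changes.

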3.3 Inclusion Criteria

All inclusion and exclusion criteria will be reviewed by the investigator or qualified designee to ensure that the subject qualifies for the study.

Product: MK-8259

Protocol/Amendment No.: 021

VEAP ID NO: 6189

Date: 15-January-2018

All patients need to meet all of the following inclusion criteria:

1. Adult patients (>18 years of age) with definite AS (as per modified New York criteria)
2. Coxitis with BASRI-hip score 0-2
3. Newly prescribed golimumab according to usual clinical practice
4. Naïve to anti-TNFs or other biologic agents prior to initiation of golimumab as indicated by the patient's medical records
5. Patient is enrolled after the investigator's decision to treat with golimumab, but before initiation of treatment with golimumab
6. Patient was informed of the benefits and risks of golimumab as per normal practice using the product leaflet
7. Signed informed consent form

3.4 Exclusion Criteria

Patients meeting the following criteria must not be enrolled in the study:

Prior or current use of an anti-TNF or other biologic agents for any disease

1. Any contraindication to golimumab in accordance to the label of Simponi®
2. BASRI-hip score 3-4
3. Any contraindication to MRI, e.g. previous hip joint replacement, heart pace maker.

3.5 Patients Enrollment

The principles of non-interventional studies (NIS) will be used. These principles include the following regarding the enrollment and monitoring of patients:

- Patient population: AS patients with coxitis followed in normal practice, in whom golimumab has been newly prescribed, will be asked to participate in the study. In patients who have been prescribed these agents the moment of prescription is normally separated from the moment the agents are administered (e.g. administrative procedures, day-clinic visit to be scheduled, retrieval of the medicine at the pharmacist, etc.). For the study, the informed consent form (ICF) will be presented at the visit during which the medicine is administered. After signing the ICF those patients agreeing to participate will be followed for approximately 24 months following the initiation of the newly prescribed medicine
- Informed consent form: Patients who have received a prescription for golimumab can be included after signing an ICF and after receiving responses to all his/her questions from the investigator proposing participation in the study. As the decision to treat the patient with a medicine of interest in this study falls within routine practice and has to be completed prior to the decision to include the patient in the study, the ICF will not provide any information on potential benefits or risks of the drug prescribed. The patient should have been informed about drug benefits and risks as per normal practice using the drug leaflet with data from actual registered label of Simponi® (golimumab) prior to inclusion in the NIS.

Product: MK-8259
Protocol/Amendment No.: 021
VEAP ID NO: 6189
Date: 15-January-2018

4 Variables and Epidemiological Measurements

4.1 Patient Demographics

The following demographic parameters will be recorded at baseline:

- Age
- Gender
- Weight
- Employment status

4.2 Treatment of golimumab and end of treatment

Data on golimumab usage as well as reasons for discontinuation of treatment will be collected at baseline and at 6, 12, 18, 24 months.

Reasons for discontinuation are withdrawal of the informed consent form by the patient for any reason, decision of the investigator to stop administration of golimumab due to safety concerns and/or due to lack of efficacy.

4.3 Clinical and Behavioral Variables

The following clinical parameters will be recorded:

- AS diagnosis duration at baseline
- Coxitis symptoms duration at baseline
- BASFI at baseline and 6, 12, 18, 24 months
- BASMI at baseline and 6, 12, 18, 24 months
- ASDAS-CRP at baseline and 6, 12, 18, 24 months
- BASDAI at baseline and 6, 12, 18, 24 months
- Radiologic stage of sacroiliitis at baseline
- Hip(s) X-ray imaging (BASRI hip index) at baseline and 12, 24 months
- Hip MRI and/or US at baseline and 6, 12 months
- Concomitant medication at baseline and at 6, 12, 18, 24 months
- Comorbidities at baseline

These parameters are described in more detail in the following sections. It should be noted that clinical variables collected in this non-interventional study are recommended for daily-practice clinical record keeping for the management of AS in Russia. Thus these variables are available for the majority of the AS patients in regular clinical practice and can be collected within locally applicable legal and ethical framework for non-interventional research.

4.3.1 AS diagnosis duration and coxitis symptom duration

AS diagnosis duration is defined as the time since date of first diagnosis of definite AS per modified New York criteria and will be recorded in number of months and years.

Product: MK-8259

Protocol/Amendment No.: 021

VEAP ID NO: 6189

Date: 15-January-2018

Coxitis symptom duration is defined as the time since date of first hip pain symptoms in a patient with AS and will be recorded in number of months and years.

4.3.2 Bath AS Functionality Index (BASFI)

The BASFI is a self-assessment instrument for defining and monitoring functional ability (physical functioning) in patients with AS. Contains 10 items: 8 items concerning activities referring to the functional anatomy of the patients (bending, reaching, changing position, standing, turning, and climbing steps) and 2 items assessing the patients' ability to cope with everyday life.

The BASFI is administered as a patient's self-report questionnaire. Consists of Numeric response scale (0–10) or Visual analog scale (0–10 cm) anchored by adjectival descriptors "easy" and "impossible." Are used to answer the questions which are practical for use in clinical practice. The mean of the 10 individual scales (scores) gives the BASFI score – a value between 0 and 10 with 0 reflecting no functional impairments and 10 reflecting maximal impairment. Numerical response scale is expected to be used by the physicians participating in the study.

The BASFI is a valid measure of physical function in AS patients and has good discrimination between groups and interventions. It is simple and easy to use and score, takes < 3 minutes to complete. The tool was designed for use in AS, but can also be used in the other spondylarthritides.

The BASFI is Endorsed by the Assessment of SpondyloArthritis International Society. The BASFI is the most widely used functional index for assessment of AS patients, primarily in studies of disease impact and in clinical trials. [22, 24]

4.3.3 Bath AS Metrological Index (BASMI)

The BASMI is an instrument that is typically used to assess mobility of spine and hip joints.

The BASMI consists of 5 items which are clinical measures of cervical rotation, tragus to wall distance, lumbar flexion, lumbar side flexion, and intermalleolar distance. Each item is scored from 0 to 10 based on individually defined cut points. Ranges are given as cervical rotation ($>85.0^\circ$ to $\leq 8.5^\circ$), tragus to wall (<10 cm to ≥ 38 cm), lumbar flexion (>7.0 cm to ≤ 0.7 cm), lumbar side flexion (>20.0 cm to <1.2 cm), and intermalleolar distance (≥ 120 cm to <30 cm).

The BASMI score is a sum of the 5 measures. The results can be graded as 0 – normal, 1 – moderate impairment, 2 – severe impairment. Every patient is given two attempts for every movement. The best results out of two is used for the BASMI.

The BASMI is included in the ASAS core sets as the preferred measure of spinal mobility. It has been used in clinical trials of anti-tumor necrosis factor agents in AS patients

The BASMI is valid, reproducible, and easy to perform with minimal training, giving valuable information about spinal mobility due to inflammation or structural damage. It is the measure of choice put forward by ASAS to measure spinal mobility in clinical trials. [22, 24]

4.3.4 ASDAS-CRP

ASDAS (AS Disease Activity Score) is an instrument to measure disease activity in AS based on a composite score.

Product: MK-8259

Protocol/Amendment No.: 021

VEAP ID NO: 6189

Date: 15-January-2018

The score includes patient-reported assessments of back pain, duration of morning stiffness, peripheral joint pain and/or swelling, general well-being, and a serologic marker of inflammation (erythrocyte sedimentation rate [ESR] or C-reactive protein [CRP]). The ASDAS including CRP has been presented as the preferred version and the one including ESR as the alternative version.

Patient response items and a serologic measure of inflammation are mathematically combined to give the ASDAS. Score ranges from zero (reflecting no disease activity) with the upper end of the scale being determined by the level of the CRP or ESR.

The time for the patient to complete the items is very short (estimated at <1 minute) with only 4 single-item questions. The score is most easily calculated using an online calculator or a hand-held calculator.

The ASDAS has been endorsed by the ASAS. The ASDAS has been validated in several observational cohorts and trial populations. It is emerging as the best measure of disease activity in AS on the basis of including both patient-generated items and objective measures of inflammation and on having, to date, equivalent or superior performance when compared to the BASDAI. [22, 24]

4.3.5 BASDAI

BASDAI (Bath AS Disease Activity Index) is an instrument to measure disease activity in AS based on a composite score.

The index includes patient-reported levels of back pain, fatigue, peripheral joint pain and swelling, localized tenderness, and the duration and severity of morning stiffness.

It contains 6 items with numeric response scales (0–10) or visual analog scales (VAS, 0–10 cm) anchored by adjectival descriptors “none” and “very severe.” Duration of morning stiffness is anchored by a time scale (0–2 or more hours).

The BASDAI has been endorsed by the Assessment of SpondyloArthritis international Society (ASAS) for the measurement of disease activity. The BASDAI has been the most frequently used measure of disease activity in AS patients. [22, 24]

4.3.6 X-ray imaging of the Hip(s)

Information on hip(s) X-ray will be collected for patients based on availability in the patient charts at baseline and at 12, 24 months. Focus will be to gather information on coxitis on conventional X-rays to determine BASRI-hip score:

0: no change;

1 - suspicious: focal joint space narrowing;

2 - mild: circumferential joint space narrowing >2mm;

3 - moderate: circumferential joint space narrowing \leq 2mm or bone-on-bone apposition of <2 cm;

4 - severe: bone deformity or bone-on-bone apposition of \geq 2 cm.

Product: MK-8259

Protocol/Amendment No.: 021

VEAP ID NO: 6189

Date: 15-January-2018

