2.3 Exploratory objectives

- To evaluate change of MRI signs of coxitis in AS from baseline to 12 months of therapy with golimumab in daily clinical practice
- To evaluate change of US signs of coxitis in AS from baseline to 12 months of therapy with golimumab
- To evaluate mean clinical scores (BASFI, BASMI, ASDAS-CRP, BASDAI) in subgroups of patients with or without MRI/US signs at baseline and their change at 12 months
- To evaluate occupational status of AS patients with coxitis at 12 and 24 months of therapy with golimumab in daily clinical practice

Data collected at 12 and 24 months are to be used for statistical analysis. But if these data is unavailable (e.g. due to early drop out before the final follow-up) data collected at 6 and 18 months are to be used according to analysis of last-observation-carried forward (LOCF) to minimize bias – section 8.2.1.

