3 METHODOLOGY

3.1 Summary of Study Design

This study is a non-interventional prospective observational cohort study. Patients participating after signing informed consent form will receive treatment and diagnostic procedures according to daily clinical practice conducted by his/her physician.

Visits during the study will include collection of data if already available. There are no procedures that are required as part of this study.

The study is to be conducted in multiple centers across Russia. AS patients with coxitis newly prescribed golimumab during the course of usual clinical care, will be enrolled and followed prospectively for 24 months with data collection at the approximate time points: baseline (pre-treatment) and consequent every 6 months. A time window of approximately \pm 6 weeks is envisaged for follow-up visits.

Product: MK-8259

Protocol/Amendment No.: 021

VEAP ID NO: 6189

Date: 15-January-2018

Patients will be screened and selected according to inclusion and exclusion criteria prior to enrollment. The study centers will maintain a list of all screened patients with the reasons for excluding patients being enrolled into the study.

Baseline data will be extracted from medical records (MR), if available at each treatment center. No additional interventional tests or medical procedures such as additional blood samples, X-ray or other technical investigations will be performed as a part of this study. If any data element is not available it will be reported as missing.

At baseline, data on age, gender, occupational status, AS and coxitis symptoms duration, concomitant disease, will be collected according to usual clinical practice.

C-reactive protein (CRP) is usually measured as part of the normal screening for patients prior to the initiation of a biologic agent in clinical practice. The results of this measurements will be collected. No additional blood withdrawals will be necessary for the study. CRP will be collected at baseline and at 6, 12, 18, 24 months if the measurements are available in regular clinical practice. Human leukocyte antigen B27 (HLA-B27) status (i.e. positive or negative) will be collected at baseline if available. Most AS patients will have this test performed as part of the diagnostic work-up in clinical practice.

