For disease activity the following instruments recommended for daily clinical practice will be used: BASFI, BASMI, ASDAS-CRP. These scores will be evaluated at baseline and at 6, 12, 18, 24 months.

Radiography of hip joint is used in clinical practice. BASRI hip will be collected at baseline and at 12, 24 months.

MRI (STIR (short tau inversion recovery) sequence and fat-saturated contrast-enhanced T1-weighted sequence) and ultrasonography (US) are used in clinical practice. Usually patients have either US or MRI, but sometimes physician may administer both radiology test if one of them is unsatisfactory as a diagnostic tool. Data of these tests will be collected at baseline and at 6, 12 months.

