6.1.3.9. BASRI-hip

BASRI-hip score determined based on hip(s) conventional X-ray will be recorded at screening as one of the inclusion criterion, at baseline and at 12, 24 months.

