8.2 Bias

8.2.1 Methods to Minimize Bias

Potential sources of bias are errors in recruitment, early drop out of patients from the study, deviation of administration of golimumab from the label of Simponi®.

Bias from errors in recruitment of patients can be reduced with rigorous adherence to inclusion/exclusion criteria when recruiting patients for the study.

Bias from early drop out of patients from the study can be reduced with Interim Statistical Analysis which is to be performed when at least 18 patients recruited are observed and have their tests done at 12 months. Also, patients who drop out before final follow up visit are planned to enter an analysis of last-observation-carried forward (LOCF). Data recorded on the last visits of patients will contribute to the analysis.

Deviation from the label of Simponi® are determined as delays of injections for more than 2 weeks at least 2 times per year. Data from patients with such delays are to be analyzed separately.

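### For BASRI-hip the fallback to 6- and 18-month data has no scheduled data behind it, and carrying baseline forward builds in the expected result of no progression

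*Combined protocol and SAP*

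**What the plan says.** The collection times for BASRI-hip are consistent throughout. Section 3.1 states "BASRI hip will be collected at baseline and at 12, 24 months". Section 4.3 lists "Hip(s) X-ray imaging (BASRI hip index) at baseline and 12, 24 months". Section 4.3.6 says "Information on hip(s) X-ray will be collected for patients based on availability in the patient charts at baseline and at 12, 24 months". Section 6.1.3.9 says the score "will be recorded at screening as one of the inclusion criterion, at baseline and at 12, 24 months". The flow chart in Section 5 marks screening, baseline, month 12 and month 24, and leaves months 6 and 18 blank. Films come from routine care only; Section 3.1 rules out any X-ray taken for the study.

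The missing-data rules are written as if every measure were collected every six months. Section 2.3 says that if 12- or 24-month results are unavailable, "data collected at 6 and 18 months are to be used according to analysis of last-observation-carried forward (LOCF) to minimize bias". Section 8.2.1 adds that "patients who drop out before final follow up visit are planned to enter an analysis of last-observation-carried forward (LOCF"). Section 8.2.2 extends LOCF to patients with missing data and also lets the visit after a missed one contribute. None of these makes an exception for BASRI-hip.

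Change in BASRI-hip at 12 and 24 months is a secondary endpoint (Sections 2.2 and 8.1.3). Section 1.2 gives a stable score at both times as one of the two results the study expects.

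**The concern.** BASFI, BASMI, ASDAS-CRP and BASDAI are all recorded at months 6 and 18, so the Section 2.3 fallback has data to draw on for them. BASRI-hip is the one secondary measure for which it has none.

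What remains under LOCF is an older grade. For a patient who leaves before month 12, the only grade is the baseline one. Carrying it forward records a change of exactly zero at both time points, although nothing was observed. Because the expected finding is no change, this pushes the analysis towards that finding. The plan itself treats at least two years of follow-up as necessary to study radiographic progression (Section 1.2), so a month-24 result made up partly of baseline and month-12 grades weakens the structural question.

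**Working it through.** **1. The schedule against the fallback**

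| Value missing | Source named in 2.3 | BASRI-hip scheduled there? | What is left |
|---|---|---|---|
| Month 12 | Month 6 | No | Baseline carried forward; or month 24, if the patient returns (8.2.2) |
| Month 24 | Month 18 | No | Month 12 carried forward; or baseline, if there is no month-12 grade |

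The plan does not say whether a baseline grade may be carried forward. If it may not, the patients in the first row who drop out simply have no value.

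**2. The plan's own figures (Section 8.3)**

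27 / 0.70 = 38.6, rounded up to 39; and 39 × 0.70 = 27.3. The 39 enrolled and 27 completing are reproduced. Section 8.3 gives a drop-out range of 21% to 37%.

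**3. How many patients are affected**

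Assumptions, none stated in the documents: drop-out D over 24 months at a constant rate, so retention is S(m) = (1 − D)^(m/24); and a film for every patient still attending at a scheduled time. For D = 0.30:

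- S(6) = 0.915, S(12) = 0.837, S(18) = 0.765, S(24) = 0.700.
- Baseline carried to months 12 and 24: 39 × (1 − 0.837) = 6.4.
- Month 12 carried to month 24: 39 × (0.837 − 0.700) = 5.3.
- Total without a month-24 grade: 39 × 0.30 = 11.7.
- Leaving between months 6 and 12: 39 × (0.915 − 0.837) = 3.0.
- Leaving between months 18 and 24: 39 × (0.765 − 0.700) = 2.5.

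The last two lines are the patients for whom Section 2.3 points to a visit they attended but at which BASRI-hip is not scheduled.

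**4. How far a real change would be diluted**

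Add the assumption that mean BASRI-hip changes linearly over time. The share of the true mean change that LOCF keeps is:

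- Month 12: S(12) = 84%.
- Month 24: S(24) + 0.5 × [S(12) − S(24)] = 0.700 + 0.5 × 0.137 = 77%.

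If a film also existed at months 6 and 18 for everyone attending, and LOCF were kept:

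- Month 12: 0.837 + 0.5 × 0.078 = 88%.
- Month 24: 0.700 + 0.75 × 0.065 + 0.5 × 0.071 + 0.25 × 0.078 = 80%.

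| Drop-out | Baseline carried | Month 12 carried to 24 | Kept at month 12: plan → with 6/18 films | Kept at month 24: plan → with 6/18 films |
|---|---|---|---|---|
| 21% | 4.3 | 3.9 | 89% → 92% | 84% → 86% |
| 30% | 6.4 | 5.3 | 84% → 88% | 77% → 80% |
| 37% | 8.0 | 6.4 | 79% → 84% | 71% → 76% |

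Most of the dilution therefore comes from carrying old grades forward, not from the absence of 6- and 18-month films. Because films are collected only if available, some attending patients will also lack one. The counts in step 3 would then be higher, by an amount the documents do not allow one to estimate.

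**The case against.** The best case for the plan is that this is a wording mismatch with little effect. The Section 2.3 sentence stands under the exploratory objectives. LOCF in 8.2.1 and 8.2.2 is general, and routes other than months 6 and 18 remain open. Annual films suit a slowly changing score: Section 1.1 cites one study with BASRI-hip unchanged over 12 months and another with it unchanged over about six years. Section 8.2.2 also promises a separate look at completers and drop-outs. Even complete 6- and 18-month films would move the retained change by only 3 to 4 percentage points at 30% drop-out.

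Much of this stands. LOCF as a whole does not fail; only the 6/18-month route does. The gain from extra films is modest at best. But the Section 2.3 sentence covers 24-month data and refers to 8.2.1, so it reads as general. The routes that remain are biased or mistimed: a carried baseline is a false zero, and a month-24 grade standing in for month 12 is a year late. The completer comparison does not tell the analyst what to do in the main BASRI-hip analysis.

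A reader might go further and infer that films taken outside the visit windows are discarded, so that most routine films are lost. The documents do not support that. The tolerance of about plus or minus "6 weeks is envisaged for follow-up visits" applies to visits, not to film dates. Section 4.3.6 collects what is available in the chart, so a film taken between visits may still be picked up at month 12 or 24. Section 3.2 says that data from before discontinuation are collected, and the central collection in 6.1.2.4 sets no limit on film date. Nothing in the documents shows how many films exist at months 6 or 18, or when routine films are taken.

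**Conclusion.** The concern holds in a limited form. For BASRI-hip, the instruction that "data collected at 6 and 18 months are to be used" has no scheduled data behind it, and the plan gives no other rule specific to this endpoint. LOCF then rests on baseline or month-12 grades, and each carried baseline grade counts as no progression.

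At 30% drop-out, about 6 of 39 patients would have baseline carried to both time points and about 5 more would have month 12 carried to month 24. Over the plan's own range of 21% to 37%, these become about 4 to 8 and 4 to 6. The counts rest on a constant drop-out rate and a film at every scheduled visit attended; the dilution figures also assume linear change. They show the order of size and are not predictions.

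One secondary endpoint is affected. The primary BASFI endpoint is not, since BASFI is recorded at months 6 and 18.

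**What to change.** Reconcile Sections 2.3, 8.2.1 and 8.2.2 with Sections 3.1, 4.3, 4.3.6, 6.1.3.9 and the flow chart, as follows.

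- At every existing visit, including months 6 and 18, record the BASRI-hip grade and the film date from any hip X-ray already in the chart. No X-ray is taken for the study.
- Count a film as the month-12 or month-24 value only if its date lies within a window stated in advance. A rule of taking the nearest film without a window would not do: a month-18 film is equally far from both time points.
- Where no film falls in the window, report the last grade at its actual follow-up time. Do not use LOCF to impute zero change in the BASRI-hip analysis.
- Show the number of observed films at each time point.

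The cost is one more CRF field, grade entries at two visits that already take place, and possibly a few more films in the planned central read. The downside is that off-schedule films may have been prompted by symptoms, and film times will vary. Recording the date does not remove that selection, so these films should be shown separately from the in-window ones. If the sponsor prefers not to collect them, the minimum is a stated missing-data rule for BASRI-hip that does not rely on months 6 and 18 and does not treat a carried baseline as observed stability.
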